4.3 Measures to minimize/avoid bias

4.3.1 Randomization

It is planned to randomize approximately 210 subjects total (126 in Stage 1 and 84 in Stage 2) in the study.

At Stage 1, each study subject will randomly be allocated by the IWRS, at a ratio of 1:1:1, to receive every 4 weeks infusions of either IVIG 1 g/kg, IVIG 2 g/kg, or the equivalent volume of Normal Saline Solution (placebo) over a treatment period of 52 weeks. After the treatment period, a 24-week follow-up period is planned before the subject completes his/her participation in the clinical trial at the FV (Figure 2).

At Stage 2, each study subject will randomly be allocated by the IWRS, at a ratio of 1:1, to receive every 4 weeks infusions of either the selected dose of IVIG from Stage 1, or the equivalent volume of Normal Saline Solution (placebo), over a treatment period of 52 weeks. After the treatment period, a 24-week follow-up period is planned before the subject completes his/her participation in the clinical trial at the FV (Figure 3).

A 5-digit randomization number will be assigned to each subject in addition to the 7-digit subject number previously assigned by the IWRS. The randomization number will be assigned at the Enrollment Visit (EV)/Infusion Visit (IV) 1 (*i.e.* EV/IV1) at Week 0.

Additional details are located in the study file at each site and, if applicable, the local healthcare professional or agency designated pharmacy.

4.3.1.1 Stratification of randomization

Subject randomization will be stratified in 2 strata: upper extremities or lower extremities. Stratification will be based upon whether the lower extremities versus the upper extremities are considered by the principal investigator or designee subinvestigator to be the more significantly affected part of the body by PPS as assessed by physical examination at the SV (Section 4.5.2.2).

4.3.2 Blinding

This is a double-blind clinical trial. For the entire clinical trial period, participating subjects, Investigators, study staff (subinvestigators, nurses, technicians, personnel involved in the administration of the investigational product, and other personnel) and testing laboratories will be blinded to the treatment group and the identity of solutions for infusion (test or placebo). Moreover, anyone from the sponsor (with the exception of the unblinded sponsor's clinical trial materials and drug safety staff) or CRO who will be involved in site monitoring will also be blinded regarding each subject's treatment group.

Unblinded personnel will be limited to:

- People responsible for creation of the randomization list who are independent of the study conduct.
- Site pharmacists or designees responsible for preparing and blinding the investigational products.
- The independent DMC for interim analysis.
- Unblinded sponsor's clinical trial materials personnel responsible for drug supply logistics

In order to address potential unblinding due to possible predictable side effects of the active product and product appearance, the following approaches will be employed:

- Pre-medication will be administered for subjects in all treatment arms and on both days of infusion to reduce the side effects of IVIG (see Section 7.2),
- All subjects will receive the same total dose volume (calculated to be equivalent to 2 g/kg Flebogamma® 5% DIF volume) for all treatments,
- Intravenous solution bags containing the investigational product solutions (test or placebo) will be covered with non-transparent sleeves,
- Connection between intravenous bag and intravenous line will be performed by unblinded staff to maintain the blind,
- Translucent or coloured lines will be used to maintain blind of the infusion system during the administration of the investigational product, and
- An independent assessor (neurologist or qualified personnel who will only have access to the efficacy data) will perform the evaluation of the efficacy endpoints. The independent assessor will not have any access to safety or AE data.

Except in the circumstances detailed in Section 5.6, the randomization code will not be broken until data entry is completed, validity of data is checked, all queries are resolved, each subject's populations for statistical analysis is agreed, and the database is locked.

4.4 Description of the investigational products

- 4.4.1 Investigational products identification
- 4.4.1.1 Investigational product (test): Flebogamma® 5% DIF

Drug name: Flebogamma[®] 5% DIF.

ATC code: J06BA 02.

Active principle: Human intravenous immune globulin.

Pharmaceutical form:

Vials containing a liquid presentation of

Flebogamma[®] 5% DIF.

Instituto Grifols, S.A.

Manufacture and

[name].

marketing

[name].

authorization holder:

Barcelona (SPAIN).

S	
	
25	
J	

Bioscience Industrial Group

4.4.1.2 Investigational product (placebo): Normal Saline Solution

Drug name: Normal Saline Solution.

ATC code: B05BB 01.

Active principle: Sodium chloride 9 g/L.

Pharmaceutical form: Vials containing Normal Saline Solution.

Manufacture and

marketing

authorization holder:

Sourced locally by study sites, thus will have marketing authorization in the country of use.

4.4.2 Dosage and dosage regimen of the investigational products

4.4.2.1 Dosage of investigational product (test): Flebogamma® 5% DIF

Dosage and regimen:	2 g/kg body weight administered over 2 consecutive days (1 g/kg infused on Day 1 and 1 g/kg infused on Day 2).
	1 g/kg body weight administered on 1 day (Day 1 or Day 2) (if randomized to IVIG 1 g/kg arm)

Administration via: Intravenously.

Administration form: Investigational product will be prepared and administered per Pharmacy Manual.

4.4.2.2 Dosage of investigational product (placebo): Normal Saline Solution

Decage and vegiment	40 mL/kg body weight administered over 2 consecutive days (20 mL/kg on Day 1 and 20 mL/kg on Day 2)
Dosage and regimen:	20 mL/kg body weight administered on 1 day (Day 1 or Day 2) (if randomized to IVIG 1 g/kg arm)
Administration via:	Intravenously.
Administration form:	Investigational product will be prepared and

4.4.2.3 Dosage regimen of investigational product (test and placebo)

At Stage 1, Flebogamma[®] 5% DIF at a dosage of 2 g/kg body weight (IVIG 2 g/kg arm), Flebogamma[®] 5% DIF at a dosage of 1 g/kg body weight (IVIG 1g/kg arm), and Normal Saline Solution (placebo) will be administered every 4 weeks, with each dose being

administered over a dosing period of 2 consecutive days (Day 1 and Day 2) up to 13 infusions visits, that is, 26 intravenous infusions.

For the purpose of maintaining the treatment blind, the volume of each administration of investigational product in the IVIG 1 g/kg and placebo arms will be equivalent to that for the IVIG 2 g/kg arm so that all subjects receive the same total dose volume for all treatment arms. The total volume for each dose of investigational product will be administered over 2 consecutive days as follows:

- IVIG 2 g/kg arm A total dose of 2 g/kg of body weight of Flebogamma® 5% DIF will be administered over 2 consecutive days.
- IVIG 1 g/kg arm A total dose of 1 g/kg of body weight of Flebogamma[®] 5% DIF will be administered on 1 day, and a total dose of 20 mL/kg of body weight Normal Saline Solution (equivalent volume of 1 g/kg of body weight Flebogamma® 5% DIF infusions) will be administered on a separate day, for a total dosing period of 2 consecutive days. The order of 1 g/kg of body weight of Flebogamma® 5% DIF or 20 mL/kg of body weight Normal Saline Solution infused on 2 consecutive days will be randomly determined for each subject by the IWRS, which will remain the same for the subject for all infusion visits during the treatment period.
- Placebo arm A total dose of 40 mL/kg of body weight Normal Saline Solution (equivalent volume of 2 g/kg of body weight Flebogamma® 5% DIF infusions) will be administered over 2 consecutive days.

Randomized Treatment Assignment	Day 1 (Day 1 Dose per IWRS Randomization list)	Day 2 (Day 2 Dose per IWRS Randomization list)
IVIG 2 g/kg	1g/kg Flebogamma® 5% DIF	1g/kg Flebogamma® 5% DIF
IVIG 1 g/kg	1g/kg Flebogamma [®] 5% DIF OR 20 mL/kg Normal Saline as determined by the IWRS (the opposite treatment as Day 2)	1g/kg Flebogamma [®] 5% DIF OR 20 mL/kg Normal Saline as determined by the IWRS (the opposite treatment as Day 1)
Placebo	20 mL/kg Normal Saline	20 mL/kg Normal Saline

At Stage 2, Flebogamma[®] 5% DIF at the selected dosage from Stage 1 and Normal Saline Solution (placebo) will be administered every 4 weeks, with each dose being administered over a 2-day dosing period. During Stage 2, the selected dose of Flebogamma[®] 5% DIF and Normal Saline Solution (placebo) will be administered over 2 days in the same manner as in Stage 1, including administering the total dose for both treatment arms at a volume equivalent to that for the IVIG 2 g/kg arm, regardless of the selected dose.

The unblinded pharmacist or designee will be responsible for preparing and blinding the investigational product (test or placebo) at each scheduled administration.

Only blinded study staff will administer the investigational product. Dosing, including infusion volumes, will be registered in the electronic Case Report Form (eCRF) by the study staff and will be available for monitors to verify compliance.

All doses after the first infusion will be administered every 4 weeks with a window period of ± 1 week.

4.4.3 Packaging and labeling of the investigational products

4.4.3.1 Investigational product (test): Flebogamma® 5% DIF

Instituto Grifols, S.A., will supply Flebogamma[®] 5% DIF free of charge. Flebogamma[®] 5% DIF will be supplied in type II glass vials containing a liquid presentation of human intravenous immune globulin for Flebogamma[®] 5% DIF.

Flebogamma[®] 5% DIF supplies will be appropriately packaged and labeled. A label sample is annexed to the clinical trial protocol (ANNEX 3). Labels will be translated into local languages.

4.4.3.2 Investigational product (placebo): Normal Saline Solution

Normal Saline Solution (9 g/L sodium chloride) is commercially available and will be sourced locally by the study sites and therefore will have marketing authorization in the country of use.

4.4.4 Storage, preparation, dispensation and administration of the investigational products

Details regarding the storage, preparation, dispensation, and administration of the investigational products are provide in the study Pharmacy Manual.

4.4.4.1 Storage and preparation of the investigational product (test): Flebogamma® 5% DIF

The unblinded pharmacist or designee will be responsible for storage, preparation and blinding of the investigational product (Flebogamma[®] 5% DIF).

Flebogamma® 5% DIF storage:

Unopened Flebogamma[®] 5% DIF vials must be stored at +2 to +25°C (+35.6°F to +77°F) and must not be frozen. It must not be used after the expiry date stated on the label. Flebogamma[®] 5% DIF must be kept in a secure room with access restricted to necessary study site personnel. The pharmacist or designee must keep the investigational product accountability by means of *the IWRS Drug Accountability Log*. Reference the Pharmacy Manual for additional information on investigation product accountability.

Flebogamma[®] 5% DIF solution preparation:

Flebogamma® 5% DIF solution will be prepared according to detailed instructions included in the SPC (ANNEX 2) and the study Pharmacy Manual.

Maximum asepsis must be kept when preparing Flebogamma[®] 5% DIF solution. It is highly recommended that if large doses are to be administered, several vials from the same batch of Flebogamma[®] 5% DIF may be pooled into an empty transparent sterile intravenous solution container (infusion bag) by using aseptic technique, preferably in laminar-flow cabins. Unblinded pharmacist or designee should inspect the solution visually for particulate matter

and color prior to solution preparation. If particles are detected or it is turbid, the vial should not be used. Any vial that has been entered should be used promptly. Because the solution contains no preservative, Flebogamma® 5% DIF should be infused as soon as possible.

The infusion bag will be covered with a non-transparent bag to blind the content of the intravenous bag. This non-transparent bag will be labeled with the clinical trial code, the patient code, the volume of solution to be infused, and additional details per the Pharmacy Manual.

The unblinded pharmacist or designee must complete a preparation register for every preparation of Flebogamma® 5% DIF solution in the IWRS. This register must be kept confidential during the clinical trial.

In case of refrigerated solutions, they must be brought to room temperature before infusion.

IMPORTANT:

The removable part of the labels of investigational products, used to prepare the Flebogamma[®] 5% DIF solution, should be stuck on the appropriate form in the Pharmacy Manual for accountability reconciliation by the clinical monitor before being destroyed.

4.4.4.2 Storage and preparation of the investigational product (placebo): Normal Saline Solution

The unblinded pharmacist or designee will be responsible for storage, preparation and blinding of the investigational product (Normal Saline Solution).

Normal Saline Solution storage:

Normal Saline Solution does not need special storage conditions. Do not use after the expiry date stated on the label. It must be kept in a secure room with access restricted to necessary study site personnel. The unblinded pharmacist or designee must keep the investigational product accountability by means of the IWRS and the Pharmacy Manual.

Normal Saline Solution preparation:

Normal Saline Solution should be prepared according to detailed instructions included in the Pharmacy Manual.

Maximum asepsis must be kept when preparing Normal Saline Solution. Once the container has been opened, the product must be transferred immediately. Unused contents must be discarded. It is highly recommended that Normal Saline Solution will be transferred into a transparent and sterile intravenous solution container (intravenous bag) by using aseptic technique, preferably in laminar-flow cabins. The unblinded pharmacist or designee must ensure that the prepared Normal Saline Solution is clear and without precipitates. Otherwise, the solution must not be administered.

The infusion bag will be covered with a non-transparent bag to blind the content of the intravenous bag. This non-transparent bag will be labeled with the clinical trial code, the patient code and the volume of solution to infuse, and additional details per the Pharmacy Manual.

As a rule, Normal Saline Solution should be administered intravenously as soon as possible after the solution transfer.

The unblinded pharmacist or designee must complete a preparation register for every preparation of Normal Saline Solution in the IWRS. This register must be kept confidential during the clinical trial.

In case of refrigerated solutions, they must be brought to room temperature before infusion.

4.4.4.3 Dispensation and administration of the investigational product (test and placebo)

The unblinded pharmacist or designee will be responsible for dispensation of the investigational product (test and placebo).

Investigational product (test and placebo) dispensation:

The unblinded pharmacist or designee will serve, attending to Investigator requests, the investigational product (test or placebo). The unblinded pharmacist or designee responsible for serving the investigational product must log into the IWRS to obtain the randomized treatment assignment for each subject preparation and dispensing.

Investigational product (test and placebo) administration:

To attenuate infusion-related events and to maintain blinding, all subjects will be pre-medicated 30-60 minutes prior to each investigational product infusion with 975-1000 mg of acetaminophen and 20-25 mg of diphenhydramine (or the equivalent dose of the available antihistaminic drug) provided the subject has no known previous history of allergies to these medications. Use of the following drugs as pre-infusion medication for the investigational product administration is not allowed: acetyl salicylic acid (ASA; e.g., aspirin), non-steroidal anti-inflammatory drugs (NSAIDS), or corticosteroids (except for inhaled corticosteroids taken for asthma which will be allowed on-demand).

The investigational product must be at room temperature prior to intravenous administration. An in-line filter with a pore size of 15 to 20 microns is recommended for the infusion. Antibacterial filters (0.2 micron) may also be used; although, they may slow infusions. Blinded study staff will administer the investigational product (test or placebo), keeping maximum asepsis, at the investigational site facilities. Administration of investigational product outside of the investigational site facilities, e.g., at the subject's home or at an outpatient clinic, is not allowed. They must also complete an administration register in order to check treatment compliance in the eCRF.

Flebogamma[®] 5% DIF administered at a dosage of 2 g/kg body weight (IVIG 2 g/kg arm) will be infused over 2 consecutive days with a maximum of Flebogamma[®] 5% DIF 1 g/kg/day (Table 2).

Flebogamma[®] 5% DIF administered at a dosage of 1 g/kg body weight (IVIG 1 g/kg arm) will be infused on 1 day with a maximum of Flebogamma[®] 5% DIF 1 g/kg/day (Table 3). To maintain the blind, a total dose of 20 mL/kg of body weight Normal Saline Solution (equivalent volume of 1 g/kg of body weight Flebogamma[®] 5% DIF infusions) will also be administered on a separate day (Table 4), for a total dosing period of 2 consecutive days. The order of 1 g/kg of body weight of Flebogamma[®] 5% DIF or 20 mL/kg of body weight

Normal Saline Solution infused on 2 consecutive days will be randomly determined for each subject by the IWRS, which will remain the same for the subject for all infusion visits during the treatment period.

Normal Saline Solution administered at a dosage of 40 mL/kg body weight (placebo arm) will be infused over 2 consecutive days with a maximum of 20 mL/kg of body weight/day (Table 5).

Summary of IVIG 2 g/kg arm's dose to be administered according to body Table 2. weight

	Flebogamma® 5% DI	F (2 g/kg body weight)	Maximum daily dose
Body weight	IVIG (g)	IVIG (mL)	(mL) of Flebogamma [®] 5% DIF (20 mL/kg body
40.1	00 -	1.600T	weight/day)
40 kg	80 g	1600 mL	800 mL
50 kg	100 g	2000 mL	1000 mL
60 kg	120 g	2400 mL	1200 mL
70 kg	140 g	2800 mL	1400 mL
80 kg	160 g	3200 mL	1600 mL
90 kg	180 g	3600 mL	1800 mL
100 kg	200 g	4000 mL	2000 mL
110 kg	220 g	4400 mL	2200 mL

Summary of IVIG 1 g/kg arm's dose of Flebogamma® 5% DIF to be administered according to body weight

	Flebogamma® 5% D	IF (1 g/kg body weight)	Maximum daily dose (mL) of Flebogamma®					
Body weight	IVIG (g)	IVIG (mL)	5% DIF (20 mL/kg body weight/day)					
40 kg	40 g	800 mL	800 mL					
50 kg	50 g	1000 mL	1000 mL					
60 kg	60 g	1200 mL	1200 mL					
70 kg	70 g	1400 mL	1400 mL					
80 kg	80 g	1600 mL	1600 mL					
90 kg	90 g	1800 mL	1800 mL					
100 kg	100 g	2000 mL	2000 mL					
110 kg	110 g	2200 mL	2200 mL					

Table 4. Summary of IVIG 1 g/kg arm's dose of normal saline solution to be administered according to body weight

Body weight	Normal Saline Solution (20 mL/kg body weight)	Maximum daily dose (mL) of Normal Saline Solution (20 mL/kg body weight/day)
40 kg	800 mL	800 mL
50 kg	1000 mL	1000 mL
60 kg	1200 mL	1200 mL
70 kg	1400 mL	1400 mL
80 kg	1600 mL	1600 mL
90 kg	1800 mL	1800 mL
100 kg	2000 mL	2000 mL
110 kg	2200 mL	2200 mL

Table 5. Summary of placebo dose to be administered according to body weight

Body weight	Normal Saline Solution (40 mL/kg body weight)	Maximum daily dose (mL) of Normal Saline Solution (20 mL/kg body weight/day)
40 kg	1600 mL	800 mL
50 kg	2000 mL	1000 mL
60 kg	2400 mL	1200 mL
70 kg	2800 mL	1400 mL
80 kg	3200 mL	1600 mL
90 kg	3600 mL	1800 mL
100 kg	4000 mL	2000 mL
110 kg	4400 mL	2200 mL

During all treatment infusions, subject's vital signs, that is body temperature (T), respiratory rate (RR), heart rate (HR), systolic blood pressure (SBP) and diastolic blood pressure (DBP), will be monitored and recorded as follows: (1) within 20 minutes before the beginning of each infusion; (2) every 30 ± 10 minutes during the first hour of each infusion; and (3) at 30 \pm 10 minutes post-completion of each infusion.

Investigational products (test and placebo) will be administered intravenously at an initial rate of 0.01 mL/kg/min for the first thirty minutes. If tolerated, advance to 0.02 mL/kg/min for the second 30 minutes. Again, if tolerated, advance to 0.04 mL/kg/min for the third 30 minutes. If the patient tolerates the infusion well, additional increments of 0.02 mL/kg/min may be made at 30-minute intervals up to a maximum of 0.08 mL/kg/min.

Individuals with predisposition to acute renal failure (such as age greater than 65 years, preexisting renal insufficiency, diabetes mellitus, hypovolaemia, overweight, concomitant nephrotoxic medicinal products), their renal function will be assessed by means of the glomerular filtration rate (GFR) at scheduled visits (see Section 4.5.2.7). Subjects with predisposition to acute renal failure but normal GFR will be infused as indicated in the previous paragraph. Subjects with predisposition to acute renal failure and abnormal GFR will be infused at the minimum practicable rate. Do not exceed the recommended dose and administer IGIV3I Grifols 5% at the minimum dose and infusion rate practicable and at less than 0.06 mL/kg/minute (3 mg/kg/minute).

The rate of infusion should be controlled by means of an infusion pump.

If an infusional AE (see Section 4.5.2.24) occurs during the first treatment course, the study staff will initiate 1 of the following actions which will be graded from 1 to 5 depending on the nature and/or severity of the event:

- 1. Does not modify the rate of the infusion upon evaluation; or
- 2. Staff reduces the current infusion rate to one-half the rate of the infusion at which the AE was observed; or
- 3. Staff progressively reduces the rate of the infusion more than one-half the rate at which the AE was observed, as necessary to subside symptoms; or
- Staff reduces the rate of the infusion to one-half, or progressively reduces more than one-half the rate at which the AE was observed, and then stops the infusion, as necessary to subside symptoms; or
- 5. Staff directly stops the infusion to subside symptoms.

The study staff will evaluate the subject's AE and then:

- Will increase or resume the infusion at a rate tolerated by the subject once the symptoms have been subsided; or
- Will stop the infusion and not resume it.

To resume the infusion, the mandatory infusion rate titration schedule must be followed. To increase the infusion rate, the initial increment must be of 0.01 mL/kg/minute for 30 minutes. If well tolerated (no infusional AE occurs), additional increments of 0.02 mL/kg/minute must be made at 30-minute intervals up to a maximum rate of 0.08 mL/kg/minute.

If a subject has an infusional AE at the same infusion rate twice, then subsequent infusion escalations, if any, should be halted at the previously highest tolerated rate.

Infusional AEs (*i.e.*, AEs temporally associated with an infusion of the investigational product) may include, but are not limited to: headache, fever, chills, shaking, fatigue, malaise, muscle cramps, abdominal cramps, back pain, abdominal pain, blood pressure changes, tachycardia, palpitations, chest tightness, nausea, vomiting, diarrhea, cutaneous reactions, rash, edema, flushing, infusion site reaction, wheezing, arthralgia, anaphylactic reaction, non-cardiogenic pulmonary edema (transfusion-related acute lung injury), thromboembolic events, renal failure, hemolysis and blood hyperviscosity.

For AEs that occur during infusions, the infusion rate in effect at the time of onset of the AE, the time of onset of the AE and the time of AE change materially in intensity and/or resolve will be captured.

SIUJIGJ	Number	GLB-PRT-FLB-IG1104	Version	0.7	Status	Effective	Effective Date	07-Mar-2022
CNICOLS	IG1104 - A n	multicenter, prospective, randomized, placebo-controlled,	, double-blind,	, parallel-gro	oup clinical trial	to assess the efficacy	0	00.4
Bioscience Industrial Group	and safety o	of Immune Globulin Intravenous (Human) Flebogamma® t	5% DIF in pat	ients with P	s with Post-Polio Syndr	оше	rage e	271 10 00

4.5 Expected duration of subject's participation and description of the sequence and duration of all trial periods

The total duration of a subject's participation for subjects who complete the study will be approximately 80 weeks. Individuals will finish their clinical trial participation with the FV (Week 76).

Each stage of the clinical trial will consist of the following periods:

- 1. Screening period (up to 4 weeks).
- 2. Treatment period (52 weeks).
- 3. Follow-up period (24 weeks).

Clinical trial finalization will coincide with the last visit of the last subject included in the study.

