2 BACKGROUND INFORMATION

2.1 Name and description of the investigational products

The following investigational products will be used in this clinical trial (Table 1):

Table 1. Investigational products

INVI	ESTIGATIONAL PRODUCTS
Test: Flebogamma® 5% DIF	Vials containing liquid preparation of Intravenous Immune Globulin (human) 5% (50 g/L)
Control (placebo): Normal Saline Solution	Containers (per study site source) of sodium chloride solution (0.9 g per 100 mL) for infusion.

Flebogamma® 5% DIF will be the investigational product being tested, and Normal Saline Solution will be the investigational product used as control (placebo).

Flebogamma[®] DIF is a sterile and liquid preparation of human immune globulin G highly purified from human plasma intended for intravenous administration. Flebogamma[®] DIF is formulated at 5% and 10% concentrations. Production process is the same until the final concentration step; bulk product is adjusted to yield desired product strength. This clinical trial (Protocol code: IG1104) is to be performed with Flebogamma[®] DIF formulated at 5% (Flebogamma[®] 5% DIF).

Normal Saline Solution will be a sterile preparation of 0.9 % sodium chloride commercially available in the corresponding country.

2.2 Summary of findings from nonclinical studies and clinical trials that are relevant to the trial

Nonclinical and clinical data related to Flebogamma® 5% DIF are summarized in the Summary of Product Characteristics (SPC) (ANNEX 2).

Safety of the isotonic sodium chloride solutions is well-known in the fluid therapy field worldwide, thanks to the existing wide experience in the use of these solutions as hydroelectrolytic balance restorer.

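### For subjects with renal predisposition and abnormal GFR, Protocol 4.4.4.3 uses an undefined product name and asks for a minimum dose, although dose is fixed by randomised arm

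*Protocol*

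**What the plan says.** Protocol 2.1 and Table 1 name two investigational products. The protocol states that "5% DIF will be the investigational product being tested, and Normal Saline Solution will be the investigational product used as control (placebo", and Section 4.4.1 identifies the same two and no other.

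The dose is set per kg by randomised arm. Section 4.4.2.1 gives "2 g/kg body weight administered over 2 consecutive days (1 g/kg infused on Day 1 and 1 g/kg infused on Day 2" for one arm and "1 g/kg body weight administered on 1 day (Day 1 or Day 2) (if randomized to IVIG 1 g/kg arm" for the other. Sections 4.4.2.3 and 7.1 repeat this, and Tables 2 to 5 turn it into one amount per weight and arm. Section 4.3.2 holds total volume at the 2 g/kg equivalent for everyone, as a blinding measure.

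Section 4.4.4.3 then deals with subjects predisposed to acute renal failure. With a normal GFR they follow the general titration. Otherwise, "Subjects with predisposition to acute renal failure and abnormal GFR will be infused at the minimum practicable rate". The next sentence says not to go above a recommended dose and to "administer IGIV3I Grifols 5% at the minimum dose and infusion rate practicable and at less than 0.06 mL/kg/minute", a limit it also gives as 3 mg/kg/minute.

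This text governs treatment. Section 2.3 admits subjects predisposed to acute renal failure on condition that they are infused as Section 4.4.4.3 indicates.

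**The concern.** Two things in that last sentence do not match the rest of the protocol.

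- **The name.** IGIV3I Grifols 5% occurs once. It is absent from Table 1, from Section 4.4.1 and from the abbreviation list, and nothing equates it with Flebogamma 5% DIF. The rest of the section speaks of the investigational product, test and placebo. The sentence therefore leaves open how it applies to placebo subjects, whose infusions are given by the same blinded staff.
- **The dose.** The preceding sentence limits rate only. This one adds dose, although the protocol contains no reduced dose for any subgroup.

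The group can enter the trial. Exclusion criterion 19 removes serum creatinine above 1.5 times the upper limit of normal, but no criterion excludes on GFR, and ages up to 75 are eligible. At stake are the clarity of a renal-safety instruction and, if a site did reduce a dose because of it, knowing which subjects received less than their randomised amount.

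**Working it through.** **1. Is the stated rate limit internally consistent?** Table 1 describes the test product as "Intravenous Immune Globulin (human) 5% (50 g/L"), which is 50 mg/mL.

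- Subgroup limit: 0.06 mL/kg/min × 50 mg/mL = 3.0 mg/kg/min. This reproduces the plan's own pair of figures.
- General maximum in the same section: 0.08 × 50 = 4.0 mg/kg/min.

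The subgroup limit is a restriction inside the general maximum, so the two rates do not contradict each other. The mg/kg figure fits a product of the test product's strength.

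**2. Are the dose tables consistent with fixed dosing?** Volume = dose in g/kg × weight ÷ 0.05 g/mL. At 70 kg:

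| Arm | Amount | Volume |
|---|---|---|
| 2 g/kg | 140 g | 140 ÷ 0.05 = 2800 mL |
| 1 g/kg, active day | 70 g | 70 ÷ 0.05 = 1400 mL |
| 1 g/kg, saline day | – | 20 × 70 = 1400 mL |
| Placebo | – | 40 × 70 = 2800 mL |

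Every row of Tables 2 to 5 reproduces in this way. Each gives one amount per weight and arm, and none has a minimum-dose column.

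**3. Can the rate limit and the full dose both be followed?** The daily volume is 20 mL/kg, with titration in 30-minute steps.

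- Cap 0.08: the steps at 0.01, 0.02, 0.04 and 0.06 deliver 0.3 + 0.6 + 1.2 + 1.8 = 3.9 mL/kg in 120 min. The remaining 16.1 ÷ 0.08 = 201.25 min, for a total of 321.25 min.
- At the 0.06 limit: the steps at 0.01, 0.02 and 0.04 deliver 0.3 + 0.6 + 1.2 = 2.1 mL/kg in 90 min. The remaining 17.9 ÷ 0.06 = 298.3 min, for a total of 388.3 min.

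The limit costs about 67 minutes per infusion day, and slightly more if the rate is kept strictly below it. It does not require a smaller dose. The conflict therefore lies in the word for dose, not in the rate.

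**4. Would the planned tables show a reduced dose?** SAP 9.2 computes volume compliance as volume infused ÷ volume prepared, and treats the prepared volume as the weight-based intended volume. As an illustration only, take a 70 kg subject whose weight-based volume is 2800 mL but for whom 1400 mL is prepared and infused. SAP 9.2 gives 1400 ÷ 1400 = 100%. Against the weight-based volume it is 1400 ÷ 2800 = 50%. SAP 9.3 summarises total volume infused in litres, so the shortfall is in the data but is not set against weight.

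**5. How many subjects?** The documents give no count of subjects with both predisposition and abnormal GFR, and none for whom a dose was altered. No size can be computed.

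**The case against.** The case for treating this as editorial is substantial, and much of it stands.

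- **A reader might infer that a different product would be given.** The documents do not support that. The name may be another term for the test product; the 5% strength and the 3 mg/kg/min conversion both fit. The sponsor supplies Flebogamma 5% DIF, sites source the saline, and an unblinded pharmacist dispenses from the interactive web response system (IWRS) assignment. No route to a wrong product is visible.
- **A reader might infer that sites cannot obey both rules.** That is too strong. The rate rule and the randomised dose can be followed together. Since the sentence opens by warning against exceeding a recommended dose, it can be read as meaning no more than the assigned dose. The Pharmacy Manual, which is not among the documents, may also settle the matter.
- **A reader might infer that the 1 versus 2 g/kg contrast was diluted.** No passage sets out a reduced dose, no count exists, and the effect cannot be bounded.
- **A reader might infer that under-dosing would escape notice.** The major-deviation lists in Protocol 10.6.1 and SAP 5.2 are open-ended, infused volumes go into the eCRF, and Protocol 5.5 requires reasons for departures from the expected dispensing regimen.
- **Early termination.** The SAP dates that decision to July 2022 and is itself effective August 2023, so a wording change now has little effect on dosing.

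None of this removes the inconsistency. A reading that rescues the sentence has to be supplied by the reader, in a paragraph on which the participation of at-risk subjects depends.

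**Conclusion.** The point holds in limited form. For subjects with both a predisposition to acute renal failure and an abnormal GFR, Section 4.4.4.3 uses a product name the protocol does not define, and refers to a minimum dose where every other dosing passage fixes dose and volume by arm. The rate limit is arithmetically correct and compatible with the full dose.

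Two assumptions carry this. The sentence names no subgroup of its own, so its scope is taken from the sentence before it. The unseen Pharmacy Manual is assumed not to resolve the wording. No endpoint, error rate, sample size or estimator is touched. Both the number of subjects and any consequence for dose selection are unknown. The weight of the point comes from its place in a renal-safety instruction and from how cheaply it can be corrected.

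**What to change.** 1. **Protocol wording.** Reconcile the paragraph in 4.4.4.3 with Sections 2.1, 4.3.2, 4.4.2 and 7.1. Use the trial's own product naming, covering test and placebo, and state how the minimum-dose wording relates to the randomised dose. Which dose or rate rule is right is for the sponsor; none is proposed here.
2. **Reporting.** In the exposure listing, identify any subject infused under this paragraph. Show whether the infused volume was below the weight-based randomised volume, so that the check does not depend on the prepared-volume denominator in SAP 9.2. If no subject was infused under the paragraph, or none received less, one sentence in the study report closes the matter.

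The cost is a wording clarification, plus one flag and one ratio from weights and infused volumes that the trial already collects.
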